Official title: Evaluation of the clinical and molecular efficacy of daily avanafil in Egyptian males with erectile and endothelial dysfunction (Randomized Placebo-Controlled study)

NCT number: NCT04374994

Document date: 20-9-2018

INTRODUCTION

Penile erection is a neurovascular process that occurs in response to the activation of pro-erectile autonomic pathways and is controlled by numerous tightly regulated events. Pathologic alteration in the endothelium of penile vasculature and/or erectile tissue and/or impairment of neurovascular processes can result in erectile dysfunction (ED).⁽¹⁾

Erectile dysfunction, the persistent inability to achieve or maintain an erection for satisfactory sexual performance, is a highly prevalent disorder associated with a significant burden of illness. The prevalence and incidence of ED are strongly age-related, affecting more than half of men >60 years.⁽²⁻⁴⁾

Erectile dysfunction is an early symptom or alert of cardiovascular disease, due to the common risk factors and pathophysiology mediated through endothelial dysfunction that may explain the association between ED and other vascular disease e.g., DM, CVD, and atherosclerosis.⁽⁴⁾

The vascular endothelium is involved in numerous physiologic functions and its dysfunction leads to impaired vasodilatation. This is attributed to decreased bioavailability of nitric oxide (NO) which is a molecule with a key role in vascular tone regulation and thus impaired NO bioactivity is a major pathogenic mechanism of ED.^(5,6)

Endothelin-1 (ET-1) is a 31-amino-acid peptide with potent and prolonged vasoconstrictor activity. It exerts its biological effect through the activation of specific endothelin receptors. Endothelin receptors have been found in human corporal smooth muscle membranes. ED was suggested to be

the result of impaired endothelium-dependent smooth muscle relaxation due to increased release of ET-1. ^(7,8)

Oral phosphodiesterase type 5 (PDE5) inhibitors are recommended as first-line therapy for ED of varying aetiology and severity. ^(9,10)

However, many patients are dissatisfied with available therapies due to high cost, adverse events and perceived lack of efficacy. Therefore, the development of novel PDE5 inhibitors with enhanced selectivity, faster onset of action, increased potency and improved tolerability is desirable. ^(11,12)

Recently, a new PDE5i, avanafil, has become available worldwide. The evaluation of safety profile suggests that avanafil is associated with a lower incidence of side effects and approved for the treatment of ED by both the US Food and Drug Administration (FDA) and the European Medicines Agency (EMA) in April 2012 and in June 2013, respectively. ⁽¹³⁻¹⁵⁾

The most important characteristic of avanafil, in comparison to the first-generation PDE5is, is its high selectivity for PDE5, particularly in relation to PDE6, PDE1, and PDE11. Avanafil has selectivity for PDE5 over PDE1 and PDE6 similar to tadalafil, but, unlike tadalafil, has negligible affinity for PDE11. ^(14,15)

AIM OF THE WORK

The aim of the work is to investigate the impact of daily avanafil on the function and levels of some soluble molecular markers of penile endothelium in men with erectile dysfunction.

PATIENTS

The study will be conducted on 140 adult males complaining of ED associated with diseases that may affect endothelial function such as diabetes mellitus, hypertension and/or dyslipidemia from outpatient clinic of Dermatology, Venereology and Andrology Department of the Alexandria main University Hospital.

They will be randomized into two groups:

Intervention group: will include seventy adult males and will receive daily avanafil for four weeks.

Control group: will include seventy adult males and will receive a placebo instead.

- An informed consent will be taken from all subjects prior to the onset of the study.
- Approval of the medical ethics committee of Alexandria Faculty of Medicine will be obtained.

Exclusion criteria:

1. Patients aged < 18 years.
2. Patients with contraindications to treatment by PDE inhibitors.
3. Patients with diseases that increase the risk of priapism (eg, leukemia and multiple myeloma).

METHODS

ALL studied groups will be subjected to:

1. Full history taking with complete general and genital examination.
2. Diagnosis and severity of ED was determined according to IIEF-5 questionnaire. Erectile dysfunction will be defined as a score of < 22 in the self reported International Index of Erectile Function-5 questionnaire (IIEF-5).⁽¹⁶⁾

The International Index of Erectile Function (IIEF-5) Questionnaire

Over the past 6 months:					
1. How do you rate your confidence that you could get and keep an erection?	Very low 1	Low 2	Moderate 3	High 4	Very high 5
2. When you had erections with sexual stimulation, how often were your erections hard enough for penetration?	Almost never/never 1	A few times (much less than half the time) 2	Sometimes (about half the time) 3	Most times (much more than half the time) 4	Almost always/always 5
3. During sexual intercourse, how often were you able	Almost never/never 1	A few times (much	Sometimes (about half the time) 3	Most times (much	Almost always/always 5

The International Index of Erectile Function (IIEF-5) Questionnaire

to maintain your erection after you had penetrated (entered) your partner?		less than half the time) 2		more than half the time)4	
4. During sexual intercourse, how difficult was it to maintain your erection to completion of intercourse?	Extremely difficult 1	Very difficult 2	Difficult 3	Slightly difficult 4	Not difficult 5
5. When you attempted sexual intercourse, how often was it satisfactory for you?	Almost never/never 1	A few times (much less than half the time) 2	Sometimes (about half the time) 3	Most times (much more than half the time) 4	Almost always/always 5

IIEF-5 scoring:

The IIEF-5 score is the sum of the ordinal responses to the 5 items.

22-25: No erectile dysfunction

17-21: Mild erectile dysfunction

The International Index of Erectile Function (IIEF-5) Questionnaire

12-16: Mild to moderate erectile dysfunction

8-11: Moderate erectile dysfunction

5-7: Severe erectile dysfunction

3. The patients in the intervention group will receive avanafil 50 mg orally for 4 weeks. They will be instructed to take their medication on an empty stomach every evening. A total of 28 pills will be prescribed at study entry and patients will be asked to count and report any unused medication at the end-of-study visit.
4. The patients in the control group will receive placebo tablets for 4 weeks.
5. Markers of endothelial function will be measured in plasma at baseline and end of treatment using standard methods and commercially available kits (Human Endothelin 1(ET-1) ELISA Kit, Nitric oxide (NO) ELISA Kit and Human Cyclic guanosine monophosphate(cGMP) ELISA Kit).⁽¹⁷⁻¹⁹⁾
6. The primary outcome will be the percentage of change of NO, cGMP and ET1 serum levels from baseline to 4 weeks posttreatment with avanafil.
7. The secondary outcome will be comparing avanafil with placebo group regarding posttreatment NO, cGMP and ET1 serum levels and percentage of change from baseline.

ETHICS OF RESEARCH

Research on human or human products:

- Prospective study: informed consent will be taken from patients. In case of incompetent patients the informed consent will be taken from the guardians.
- Retrospective study: confidentiality of records will be considered.
- DNA/genomic material: informed consent for DNA / genomic test and for research will be taken from patients. No further test will be carried out except with further approval of committee and patients. If the samples will travel outside Egypt the researcher will be responsible for transportation and security approval.
- All drugs used in the research are approved by the Egyptian Ministry of Health.

Research on animal:

- The animal species are appropriate for the test.
- After test, if animal will suffer, it will be euthanized and properly disposed.
- After operation, it will have a proper postoperative care.

RESULTS

The data will be recorded, tabulated, statistically analyzed and represented in appropriate figures and diagrams to fulfill the aim of the work.

DISCUSSION

The findings will be discussed in view of achievement of the aim. The results of other related studies will be compared to those of the current one.

REFERENCES

1. Giuliano F. New horizons in erectile and endothelial dysfunction research and therapies. *Int J Impot Res* 2008; 20:2-8.
3. McKinlay JB. The worldwide prevalence and epidemiology of erectile dysfunction. *Int J Impot Res* 2000; 12(14):6-11.
6. Lue TF. Erectile dysfunction. *N Engl J Med* 2000; 342(24):1802-13.

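### Background treatment of the diseases that qualify men for entry need not be stable and is not tracked, so its effects count as avanafil effect in the within-arm primary outcome

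*Protocol*

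**What the plan says.** The PATIENTS section of the Protocol recruits 140 men with erectile dysfunction associated with "diseases that may affect endothelial function such as diabetes mellitus, hypertension and/or dyslipidemia from outpatient clinic". It lists three exclusions: "Patients aged < 18 years"; "Patients with contraindications to treatment by PDE inhibitors"; and "Patients with diseases that increase the risk of priapism (eg, leukemia and multiple myeloma"). None of them concerns how the qualifying disease is treated, or for how long that treatment has been unchanged.

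METHODS item 1 provides for "Full history taking with complete general and genital examination", which may well capture current drugs at entry. For the end-of-study visit, item 3 asks only for the number of unused study pills. Neither document provides for recording changes in other medication between the two blood samples.

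METHODS item 6 states: "The primary outcome will be the percentage of change of NO, cGMP and ET1 serum levels from baseline to 4 weeks posttreatment with avanafil". The comparison of avanafil with placebo, on post-treatment levels and on percent change, is the secondary outcome in item 7. The SAP lists two-group tests and two-period tests, all unadjusted, and a Spearman correlation.

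**The concern.** Men enter because they have a disease that, by the Protocol's own description, may act on the endothelium, and the endpoint is a 4-week change in endothelial markers. The INTRODUCTION ties erectile dysfunction to other vascular disease through "common risk factors and pathophysiology mediated through endothelial dysfunction". A man who has just started treatment for such a disease, or whose doses are being adjusted, is eligible. If that treatment moves NO, cGMP or ET-1 between the two samples, the movement forms part of his change from baseline.

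Item 6 looks only at change on avanafil, so it cannot separate that movement from the drug's own effect. A reported rise or fall could be partly or wholly due to background treatment, or a real effect could be masked. If changes are not recorded at the visits, nobody can later say how common they were or whether they differed between arms.

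**Working it through.** The documents contain no figure to reproduce: 70 men per arm is given without a power calculation, a marker SD or an expected effect. What follows is illustration on stated assumptions.

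**Inputs from the documents.** n = 70 per arm (PATIENTS); randomised allocation; two samples, at baseline and end of treatment (METHODS item 5); 5% significance level (SAP), taken as two-sided.

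**Assumed inputs.** f is the share of men whose background treatment starts or changes. d is the resulting shift in a marker, in percentage points of change from baseline. s is the same shift in SD units of the change.

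**Step 1: shift in the primary outcome with no avanafil effect.** Shift in the arm mean = f × d.
- f = 10%, d = 10: 0.10 × 10 = 1 percentage point
- f = 25%, d = 20: 0.25 × 20 = 5 percentage points
- f = 30%, d = 30: 0.30 × 30 = 9 percentage points

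**Step 2: effect on the placebo contrast.** With equal expected f in both arms, the expected shifts cancel. What remains is chance imbalance. The SD of the between-arm difference in f is √(2 × 0.25 × 0.75 / 70) = 0.073. Multiplied by d = 20, this is about 1.5 percentage points (1 SD).

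That amount is already inside the standard error of the two-sample test. On an assumed SD of percent change of 30, the added variance is 0.25 × 0.75 × 20² = 75, so the SD becomes √(900 + 75) = 31.2, about 4% larger.

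**Step 3: false-positive rates.** For each scenario 20,000 trials were simulated with 70 men per arm, normally distributed changes and no avanafil effect. The within-arm test is the paired t-test on avanafil; the between-arm test is the two-sample t-test. Power is a normal approximation for an assumed true difference of 0.5 SD, with the SD inflated to √(1 + f(1 − f)s²). Without background changes it is 84%.

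| f | s (SD) | Within-arm rejects | Between-arm rejects, equal f | Between-arm rejects, f 10 points higher on avanafil | Between-arm power |
|---|---|---|---|---|---|
| 0.1 | 0.5 | 7.0% | 4.9% | 5.8% | 83.3% |
| 0.1 | 1.0 | 12.7% | 5.1% | 8.6% | 80.9% |
| 0.2 | 0.5 | 12.8% | 5.0% | 5.8% | 82.7% |
| 0.2 | 1.0 | 33.9% | 4.9% | 8.6% | 78.4% |
| 0.3 | 0.5 | 22.5% | 5.1% | 5.9% | 82.2% |
| 0.3 | 1.0 | 61.7% | 4.8% | 8.4% | 76.7% |
| 0.5 | 0.5 | 50.9% | 4.9% | 6.1% | 81.9% |
| 0.5 | 1.0 | 96.0% | 4.9% | 8.5% | 75.4% |

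The within-arm test loses control of its error rate as f and s grow. The between-arm test holds 5% when the rates are equal and loses some power.

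**The case against.** The strongest reply is that this is a randomised placebo-controlled trial, and the control arm exists to absorb influences of this kind. That stands for item 7: with equal rates in both arms the comparison is unbiased. A reader might infer that untracked background treatment biases the placebo comparison as well, or that the 1.5-point shift in step 2 is a bias. The documents do not support either reading. The shift is chance variation that the test already allows for. Systematic bias would need background changes to differ between arms, for example through knowledge of allocation. The documents describe a placebo without further detail on blinding or concealment, but silence is not evidence of a difference.

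A second reply is that the root cause is item 6, not the entry criteria. This also stands in large part. A stability rule alone would leave a within-arm outcome open to regression to the mean, assay drift and treatment changes during the study. A between-arm primary contrast removes the average bias without any new entry rule. It would not recover lost precision, however, or show whether changes were balanced; that takes stability and recording.

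Third, the premises go beyond the text. The Protocol says the diseases may affect endothelial function. It does not say that treating them moves these markers within 4 weeks, and the listed procedures include no glucose or lipid test that would reveal new disease at entry. This is fair, and it is why the size is left open. Baseline drug use is probably covered by the history; the clear gap in recording is at the end visit.

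**Conclusion.** The gap is real and matters for the primary outcome as worded. Selection is on diseases that may affect the endothelium, stability of their treatment is not required, changes are not recorded, and item 6 attributes the whole within-arm change to avanafil. The placebo comparison in item 7 is protected on average, at the cost of some noise and chance imbalance.

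The size cannot be established from the documents. Over the assumed ranges, the mean change on avanafil moves by 1 to 9 percentage points, and the within-arm test rejects in 7% to 96% of trials with no drug effect. The upper end requires half the men to change treatment with a shift of a full SD. The between-arm error rate stays at 4.8% to 5.1% when rates are equal and reaches about 6% to 9% if changes are 10 points more frequent in one arm. The existence of the gap does not depend on these assumptions; its importance does.

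**What to change.** 1. Add an entry criterion that antihypertensive, lipid-lowering and glucose-lowering treatment has been unchanged for a period before the baseline sample, with re-screening allowed. The sponsor should set and justify the length. Four weeks, matching the treatment period, is only an example; nothing in the documents shows that the markers settle in that time.
2. Record these drugs at baseline and at the end-of-study visit.
3. Leave medically needed changes during the study to the treating physician, and report them by arm. Any analysis that leaves those men out conditions on an event after randomisation, so it should be labelled supportive only.
4. Rest the conclusion on the avanafil-minus-placebo difference in change. This is the step that removes the average bias.

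The cost is one eligibility line, one medication question at two existing visits, and a rewording of the outcomes in METHODS items 6 and 7. The data for the between-arm comparison are already planned. The downside is that a few recently treated men enter later.

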Official title: Evaluation of the clinical and molecular efficacy of daily avanafil in Egyptian males with erectile and endothelial dysfunction (Randomized Placebo-Controlled study)

NCT number: NCT04374994

Document date: 20-9-2018

Statistical analysis of the data: Data were fed to the computer and analyzed using IBM SPSS software package version 20.0. Qualitative data were described using number and percent. Quantitative data were described using range (minimum and maximum), mean, standard deviation and median. Significance of the obtained results was judged at the 5% level. Student t-test was used for normally distributed quantitative variables, to compare between two studied groups. Mann Whitney test for abnormally distributed quantitative variables, to compare between two studied groups. Wilcoxon signed ranks test, for abnormally distributed quantitative variables, to compare between two periods. Paired t-test for normally quantitative variables, to compare between two periods Spearman coefficient for correlation between two abnormally quantitative variables.

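### The avanafil–placebo comparison leaves disease status out of the analysis: the unadjusted tests are valid on average, but they give up precision and cannot correct a chance imbalance in the trial as run

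*Protocol*

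**What the plan says.** The PATIENTS section of the protocol recruits men with "ED associated with diseases that may affect endothelial function such as diabetes mellitus, hypertension and/or dyslipidemia". METHODS item 5 treats NO, cGMP and ET-1 as markers of endothelial function, so the protocol itself links the entry diseases to what the outcomes measure. Item 8 of its reference list is titled "Endothelin-1 in diabetic and nondiabetic men with erectile dysfunction".

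On allocation the protocol states "The study will be conducted on 140 adult males" and "They will be randomized into two groups", then "Intervention group: will include seventy adult males" and "Control group: will include seventy adult males". It names no stratification factor, blocking, minimisation or method of generating the sequence.

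The between-arm comparison is METHODS item 7: "The secondary outcome will be comparing avanafil with placebo group regarding posttreatment NO, cGMP and ET1 serum levels and percentage of change from baseline". The SAP supplies the test: "Student t-test was used for normally distributed quantitative variables, to compare between two studied groups", with Mann-Whitney for variables that are not normally distributed. Its other tests are the paired t, Wilcoxon signed ranks and Spearman correlation. No regression, analysis of covariance or stratified test is planned.

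**The concern.** The avanafil–placebo contrast is the only randomised comparison in the trial. If men with and without, say, diabetes differ in marker level, that variation stays in the error term of an unadjusted test and widens the confidence interval. If one arm happens to receive more diabetic men, the estimate moves with the imbalance and neither planned test can take the shift out. The information needed is available at no extra cost, since METHODS item 1 requires a full history from every man.

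**Working it through.** **Inputs from the documents.** 140 men, 70 per arm; 5% significance level (sidedness is not stated, two-sided assumed).

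**Inputs assumed, because the documents give none.** Disease prevalence 50% (range 20–70%); difference between men with and without the disease, δ = 0.5 to 1.0 SD of the marker, total SD set to 1; correlation of baseline with follow-up, ρ = 0.3 to 0.7. The documents state no power or effect size, so there is no planned figure to reproduce. For orientation, 70 per arm detects (1.960 + 0.842) × √(2/70) = 2.802 × 0.169 = 0.474 SD with 80% power.

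**Step 1: how often imbalance occurs.** With independent arms the between-arm difference in prevalence has SD √(2 × 0.25/70) = 8.5 points. An exact 70:70 split has probability C(140,70)/2^140 = 0.067 under simple randomisation, so some restricted list may be in use. Both models are shown, the second with exactly 70 carriers among the 140 men.

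| Imbalance in one disease, 50% prevalence | Independent arms (binomial) | Arms fixed at 70:70 (hypergeometric) |
|---|---|---|
| 10 points or more (7 or more men) | 27% | 24% |
| About 17 points or more (12 or more men, e.g. 41 v 29) | 5% | 6% |

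With fixed arms the chance of 10 points or more falls to 20% at 30% or 70% prevalence, and to 14% at 20% prevalence.

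**Step 2: what a given imbalance does.** The estimate shifts by b = δ × imbalance. Its conditional standard deviation is s = 0.169 × √(1 − δ²/4), and the t-test rejects beyond c = 1.977 × 0.169 = 0.334. The conditional false-positive rate is Φ(−(c − b)/s) + Φ(−(c + b)/s). For 41 v 29 men and δ = 0.8: b = 0.8 × 12/70 = 0.137, s = 0.155, and the rate is Φ(−1.27) + Φ(−3.04) = 10%.

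| δ (SD) | Shift at 12/70 (SD) | Rate at 17 points | Rate at 10 points | Rate at exact balance |
|---|---|---|---|---|
| 0.5 | 0.09 | 7% | 5–6% | 4% |
| 0.8 | 0.14 | 10–11% | 5–6% | 3% |
| 1.0 | 0.17 | 13% | 5–6% | 2% |

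Rates above 5% in unbalanced trials are offset by rates below 5% in balanced ones. Simulated over all randomisations (three factors, 10,000 trials per scenario), the unadjusted t-test rejects in 5.1–5.3% of null trials.

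**Step 3: precision from adjusting for disease alone.** The share of variance removed is δ²/4.
- δ = 0.5: 6%. Equivalent to 140/(1 − 0.0625) − 140 = 9 extra men; detectable difference 0.474 × √0.9375 = 0.46 SD.
- δ = 0.8: 16%. Equivalent to 140/0.84 − 140 = 27 extra men; detectable difference 0.474 × √0.84 = 0.43 SD.

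**Step 4: what disease status adds once baseline marker level is in the model.** Assume the disease shifts baseline and follow-up equally. With w = 1 − δ²/4 and within-disease correlation r = (ρ − δ²/4)/w, the further saving is 1 − w(1 − r²)/(1 − ρ²).

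| δ | ρ = 0.3 | ρ = 0.5 | ρ = 0.7 |
|---|---|---|---|
| 0.5 | 4% | 2% | 1% |
| 0.8 | 10% | 6% | 3% |

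**Step 5: the same in power.** Starting from 80%, power becomes Φ(2.802/√(1 − R²) − 1.960), where R² is the share of variance explained: 81% at R² = 2%, 82% at 5%, 88% at 20%.

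**The case against.** The strongest reply is that unadjusted tests after randomisation are valid with 140 men and that adjustment is an efficiency choice. That stands. A reader might infer from the mixed population that type I error is inflated or the estimate systematically biased; Step 2 shows it is not. The error is conditional on the imbalance that happens to occur.

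A reader might also join two figures that belong to different events. At least one of three independent diseases at 50% prevalence is 10 or more points out in about 56–61% of trials, but at that size the false-positive rate is 5–6%. The 7–13% rates need about 17 points in one disease.

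Other limits also stand:
- The protocol does not say that randomisation is simple; the absence of stratification is inferred from silence.
- The primary outcome (METHODS item 6) is worded as change with avanafil, and between-arm imbalance does not enter a within-arm change. The point concerns the secondary outcome.
- The protocol says only that the diseases may affect endothelial function, and a reference title gives neither direction nor size.
- Percentage change uses each man's own baseline and may remove part of the disease difference.
- The SAP describes qualitative data by number and percent, so disease counts by arm could be shown. It would overstate the case to say that an imbalance must stay hidden.

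Two things remain. Post-treatment levels are also compared directly, where a disease difference in level enters in full. And if strata were used in the randomisation, the SAP ignores them, so the analysis half of the point holds either way.

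**Conclusion.** The point holds as a matter of precision and of error conditional on realised imbalance, in the secondary avanafil–placebo comparison. It does not show an invalid test, an inflated overall error rate or a defect in the primary outcome as worded, and it does not make stratified randomisation necessary.

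Its size depends on prognostic strength, which the documents do not give. For assumed disease effects of 0.5–0.8 SD, the gain is about 6–16% of variance without baseline adjustment and about 1–10% with it. If disease status explains 5% of variance or less, the gain is at most 2 power points. A damaging imbalance in one disease is uncommon (5–6% at 50% prevalence), but if it occurs the planned tests cannot correct it. The change is worth making because it costs almost nothing.

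**What to change.** In the SAP, pre-specify each avanafil–placebo comparison as a linear model for the post-treatment marker (log scale if skewed), with arm, baseline marker level and diabetes status (yes/no) as terms; hypertension and dyslipidaemia may be added. On the log scale, with log baseline as a covariate, the arm coefficient is the same whether the outcome is post-treatment level or change, so one model serves both parts of METHODS item 7. Where ranks are kept, use a van Elteren test stratified by diabetes, accepting that it does not adjust for baseline. Tabulate all three diseases by arm.

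In the protocol, state how the sequence is generated. If allocation has not begun, a blocked list stratified by diabetes is an optional extra. Any stratification factor used must also appear in the analysis.

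The cost is small. Residual degrees of freedom go from 138 in the t-test to 136 with baseline and diabetes, or 134 with all three diseases, and the analysis takes slightly more work. If the optional stratification is adopted, the arms may miss exactly 70:70 by up to half a block per stratum.

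### Does the end-of-treatment blood draw need a fixed interval from the last evening tablet, and one name for the specimen?

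*Protocol*

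**What the plan says.** All the relevant protocol text is in METHODS, items 3 to 7.

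- **Item 3** concerns the avanafil group: "They will be instructed to take their medication on an empty stomach every evening". Twenty-eight pills cover the four weeks, and "patients will be asked to count and report any unused medication at the end-of-study visit".
- **Item 4** gives the control group placebo tablets for four weeks, with no time of day.
- **Item 5** sets the two sampling times: "Markers of endothelial function will be measured in plasma at baseline and end of treatment".
- **Item 6**, the primary outcome, is the "percentage of change of NO, cGMP and ET1 serum levels from baseline to 4 weeks posttreatment with avanafil".
- **Item 7**, the secondary outcome, is "comparing avanafil with placebo group regarding posttreatment NO, cGMP and ET1 serum levels and percentage of change from baseline".

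The SAP supplies the within-group tests. For non-normal variables this is the "Wilcoxon signed ranks test, for abnormally distributed quantitative variables, to compare between two periods", and for normal ones the paired t-test. It does not say which two periods are meant. Neither document states a dose-to-draw interval, a sampling window, a clock time or a fasting state for the draw. The empty stomach in item 3 concerns taking the tablet.

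**The concern.** The three markers are the primary outcome, and the drug is given once each evening. Two men could both satisfy item 5 although one is bled the morning after a tablet and the other a day or more after his last one. If the effect on nitric oxide, cGMP or endothelin-1 fades between doses, their samples measure different things. A late draw dilutes the average effect. With no record of when the last tablet was taken, the analysis could not sort early draws from late ones afterwards.

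There is also a question of meaning. A change seen hours after a dose may be drug still acting, while a change that outlasts the drug would suggest a more durable effect on the endothelium. An unrecorded interval leaves the two mixed.

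Two wording points add to the unease. Item 6 could be read as four weeks after treatment stops, which would conflict with item 5. And the same three markers are measured in plasma in one item and reported as serum in the next two.

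**Working it through.** **Does the text fix the day of the draw?** Item 3 supplies 28 pills at one each evening, which is 28 / 7 = 4 weeks. Item 5 places the second measurement at the end of treatment. Item 6 counts four weeks from baseline, the same length as treatment. The documents describe no drug-free follow-up and no third sample. Reading item 6 as the end of the four-week course makes all three items agree. The SAP's two periods can then only be baseline and end of treatment, because no other pair of marker measurements exists. The day is therefore settled; the hours are not.

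**What could the missing hours cost?** The plan has no power statement, effect size or standard deviation, so there is no figure of its own to reproduce. What follows gives scale only.

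Inputs from the documents: 70 men per arm (PATIENTS) and a 5% significance level (SAP). Assumptions: two-sided testing; an ordinary draw 12 h after the last evening tablet; a late draw one day after that, at 36 h; a marker effect fading with half-life h of 48, 24, 12 or 6 h; and 80% power if every draw is at 12 h.

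1. Effect giving 80% power. Two-sample t-test, 70 per arm: d = 0.477. Paired t-test, 70 men: dz = 0.340. The normal approximation gives (1.960 + 0.842) × √(2/70) = 0.474 and (1.960 + 0.842)/√70 = 0.335.
2. Effect at 36 h relative to 12 h: f = 0.5^(24/h).
3. If a share s of men is drawn late, the mean effect is multiplied by 1 − s(1 − f). For example, with h = 24 and s = 0.10, it is 1 − 0.10 × 0.50 = 0.95.
4. Two-sample power at d times that factor:

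| Half-life | f | All late | Half late | 10% late |
|---|---|---|---|---|
| 48 h | 0.707 | 51% | 67% | 78% |
| 24 h | 0.500 | 29% | 56% | 76% |
| 12 h | 0.250 | 11% | 42% | 74% |
| 6 h | 0.0625 | 5% | 32% | 72% |
| No fading | 1 | 80% | 80% | 80% |

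With 5% late, power is 76% to 79%. When all draws are late, the paired test agrees with the two-sample test to three decimals. The extra between-man variance from mixed timing is not counted.

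The range from 5% to 80% is produced by the half-life and the late share, and the documents speak to neither. The severe entries need half or all of the men to be a full day late. Item 3's pill count does not imply that: it is an ordinary adherence check, and a leftover pill may come from any missed evening, not only the last.

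**Could timing create a false difference between arms?** Men are randomised to avanafil or placebo, and nothing in the plan ties visit timing to arm. Uneven timing of that kind adds noise or dilutes a fading effect; it does not manufacture an avanafil-placebo difference.

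**Plasma or serum?** Items 5, 6 and 7 concern the same three markers measured by the same kits. Nothing suggests that specimens change between visits or arms. With one specimen throughout, the percentage change and the group comparison stand under either label.

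**The case for a change.** The best case for acting is that the gap is real and cheap to close. The text is continuous, so nothing has been redacted here; a pill count does not show when the last tablet was taken; and timing that was never recorded cannot be recovered. The primary outcome is also worded as a change within the avanafil group. A systematic shift in clock time or fasting state between baseline and week 4 would enter that figure with no placebo correction.

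Part of this stands. The interval is unwritten, and the within-group change alone cannot remove a shift common to both arms. But item 7 compares the same percentage change with placebo, which does remove it, and nothing in the documents suggests that the two visits would be run under different conditions.

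The argument that a short-lived effect cannot be told from a lasting one also has some force, but it asks more than the trial does. The AIM OF THE WORK section concerns the impact of daily avanafil on penile endothelial function and markers. It makes no claim about an effect that outlasts the drug, so a change measured at the close of four weeks of daily use answers it.

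**Conclusion.** No change to the plan is needed. What is missing is operational detail that a clinic running an ordinary end-of-treatment visit supplies as a matter of course, and following the plan as written would still give a sound result. The day of the draw and the SAP's two periods can be inferred from items 3, 5 and 6. The plasma/serum difference is a clerical slip without effect on validity, provided that one specimen is used at both visits and in both arms.

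The size of any loss cannot be derived from the documents. Under the assumptions above, 10% of draws a day late would cost 2 to 8 percentage points of power, and no loss occurs if the effect does not fade within that time. The much larger losses need late shares that nothing in the documents supports. The conclusion rests on most draws falling within about a day of the last tablet, and on timing being unrelated to arm. Evidence that visits commonly ran late, or ran differently by arm, would reopen the question.
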